2.1. Eligibility Criteria

2.1.1. Inclusion Criteria

- a. Histologically or cytologically confirmed gastric adenocarcinoma
 - b. Metastatic disease must be measurable by CT and/or MRI
 - or*
 - There must be a history of positive peritoneal washings or carcinomatosis
 - c. All disease should be deemed resectable to negative margins (NED) based on imaging studies e.g.:
 - Esophageal invasion <4cm that does not require thoracotomy (Seiwert II and III lesions)
 - Hepatic metastases (unilateral or bilateral ≤ 5 lesions, ≤ 15 cm total diameter)
 - Primary peritoneal metastases (small disease load \leq P2 disease) without massive ascites or intestinal obstruction
 - Para-aortic lymph node metastases (stations 16 a1 and/or b2, see appendix 5)
 - Lung metastases (≤ 3 unilateral/bilateral, 9 cm total diameter)
 - Patients who present with both hepatic and peritoneal metastases must have no evidence of extensive para-aortic/retro-pancreatic lymph node metastases
- Note:** Patients with both pulmonary and peritoneal metastases will be enrolled at the discretion of the PI
- d. Greater than or equal to 18 years of age
 - e. Must be able to understand and sign the Informed Consent Document
 - f. Clinical performance status of ECOG ≤ 2
 - g. Life expectancy of greater than three months
 - h. Patients of both genders must be willing to practice birth control during and for four months after receiving chemotherapy
 - i. Hematology:
 - Absolute neutrophil count greater than $1500/\text{mm}^3$ without the support of Filgrastim.
 - Platelet count greater than $75,000/\text{mm}^3$.
 - Hemoglobin greater than 8.0 g/dl.
 - j. Chemistry:
 - Serum ALT/AST less or equal to 5 times the upper limit of normal; except in the presence of obstructive liver metastases where ALT/AST may be up to 10 times the upper limit of normal
 - Serum creatinine less than or equal to 1.5 mg/dl unless the measured creatinine clearance is greater than $60 \text{ mL/min}/1.73 \text{ m}^2$
 - Total bilirubin less than or equal to 2 mg/dl, except in the presence of obstructive metastases
 - PT within 2 seconds of the upper limit of normal (INR ≤ 1.8)
 - k. No history of prior/other malignancies within the 2 years prior to enrollment with the exception of basal cell carcinoma

2.1.2.

Exclusion Criteria

- a. Prior treatment with FOLFOXIRI (treatment with any of the components as separate regimens is allowable)

- b. Inability to tolerate any of the chemotherapeutic agents

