3.1. Staging Laparoscopy

3.1.1. Patients who meet eligibility criteria will be taken to the operating room for staging laparoscopy and peritoneal washings. At laparoscopy biopsies of the peritoneum will be done and used later to confirm status of peritoneal disease (not as a part of the staging procedure but as part of the study).

- Any suspicious lesions that might preclude resection to NED will be biopsied as well.
- Liver ultrasound to confirm axial imaging findings will be done.
- Randomization and stratification will be done after laparoscopy and only after the results of the peritoneal washings are known (within one week of laparoscopy).

3.1.2. Patients will then be randomized to receive gastrectomy and/or metastasectomy plus systemic therapy (GYMS arm) or systemic therapy alone (SA arm).

- Patients randomized to receive the standard of care (SA arm) will receive systemic therapy (as described in Section 3.5). **Note:** Patients may undergo palliative gastrectomy if indicated but must begin chemotherapy within 6 weeks of gastrectomy (8 weeks following randomization).
- Patients randomized to receive gastrectomy and/or metastasectomy plus systemic therapy (GYMS arm) will be taken to the operating room within 1-2 weeks of randomization (as soon as feasible). Patients may undergo surgery only at the NCI. Subsequently, patients will receive systemic therapy within 4 to 16 weeks after surgery and/or when fully recovered from surgery. Patients who do not recover within 16 weeks will be taken off treatment and followed for survival. (**Note:** patients who undergo thoracotomy for pulmonary metastases must be able to receive systemic therapy within 24 weeks of their initial surgery.) This is an intent-to-treat phase III trial.

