3.2. Gastrectomy, Metastasectomy, Peritonectomy and Intraperitoneal Therapy

Surgical Guidelines:

Note: The following guidelines are for the purpose of promoting consistency in the surgical procedure, and peri-operative care where possible. Physician discretion will be exercised as necessary to ensure that the specific needs of the patient are met. Details pertaining to surgical and perioperative management will be recorded in the patient medical record but will not be captured on the CRFs.

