Note: Patients at risk for splenectomy (proximal T3-T4 lesions) may receive triple vaccination (Pneumococcal, Meningococcal, *Haemophilus influenzae*) prior to surgery.

3.2.5. Hepatic metastasectomy:

- Intraoperative ultrasound will be performed on all patients to detect disease not witnessed on preoperative imaging. Unexpected findings will be recorded in the patients chart.
- The goal of hepatic metastasectomy is to render the patient NED with at least 1 cm negative margins when possible.
- The preferred modality of hepatic metastasectomy is anatomical segmental resection. For single lesions, when possible, segmentectomy should be performed. For more than a single isolated lesion, a sectorectomy or partial hepatectomy should be performed if feasible. In all cases, the surgeon should strive to obtain negative margins.

- A non-anatomic wedge resection shall be performed only for small superficial lesions deemed resectable to negative margins by intra-operative ultrasound and preoperative imaging.
- In selected cases, intraoperative RFA and/or microwave ablation may be used at the discretion of the operating surgeons if deemed in the best interests of the patient.
- Portal vein ligation/embolization should be considered in selected patients to preserve post-operative liver function.
- A formal hepatic lobectomy will be done for large lesions spanning more than two sectors, or multiple lesions within a single hepatic lobe.
- In all cases of hepatic gastric metastasis undergoing liver resection, the surgeon should perform portal and hepatic artery lymph node dissection whenever possible.

3.2.6. Peritoneal metastasectomy (cytoreductive surgery):

- If there is evidence that the extent of disease is beyond the ability to be debulked such that the largest residual tumor nodule is less than or equal to 0.5 cm, patients will be considered ineligible and removed from treatment.
- For patients with primary peritoneal metastases (small disease load; P0-P2 disease) without massive ascites or intestinal obstruction, all visible disease will be resected if technically feasible.
- Complete peritonectomy for patients with peritoneal disease includes the following: the right and left sub-diaphragmatic peritoneum, the falciform ligament, lesser and large omentum, anterior, right and left abdominal wall down to the paracolic gutters and the pelvic peritoneum.

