- Partial (limited) peritonectomy for patients with intra-abdominal disease without peritoneal disease includes (i.e., liver metastases without peritoneal disease): peritoneal attachment of the hepatic left lateral segment and the spleen, 2 cm along the incision at the anterior abdominal wall and the falciform ligament (Appendix 1).

3.2.7. Para-aortic lymph-node metastases:

- To be considered eligible for CHPP and debulking with “positive” para-aortic lymph nodes, patients will have no evidence of metastatic disease outside of para-aortic lymph nodes on preoperative imaging and no evidence of hepatic or peritoneal metastases on intraoperative examination.
- Stations 16a1 and/ or b2 will be resected when technically possible.

3.2.8. Lung metastases:

- Timing of resection will be in the best interest of each individual patient. The decision will be made by the thoracic surgeon and the GI surgeon. It can either be performed at the same time as the gastric resection or at a later time point, with a delay of no more than 16 weeks in cases of synchronous disease. **Note:** patients must begin chemotherapy within 24 weeks of randomization.
- Lung metastasectomy will follow the standard of care and as defined by the inclusion/exclusion criteria.

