3.5. Systemic Chemotherapy Therapy

3.5.1. Guidelines

Patients who randomize to receive systemic chemotherapy alone (SA) will begin treatment within 14 days of randomization; patients who undergo palliative gastrectomy will begin chemotherapy within 6-8 weeks of randomization. Patients who randomize to surgery plus chemotherapy (GYMS) will begin treatment approximately 6-8 weeks following surgery (24 weeks for patients requiring sequential thoracic and abdominal surgery). **Note:** patients must meet eligibility requirements prior to beginning chemotherapy. Patients who do not recover from the surgical procedure within the stated timeframe will be removed from treatment and followed for survival.

Systemic therapy may be administered by the patient's local oncologist in collaboration with the PI or at the NCI by the Medical Oncology Branch. Systemic therapy will follow the guidelines for the FOLFOXIRI regimen⁷⁷. Chemotherapy and supportive care will be administered in accordance with each institution's policies for the administration of chemotherapeutic agents.

During treatment, the treating oncologist will be asked to fax the following information (Appendix 8) to the research nurse (noted below) at the conclusion of every other cycle (4 weeks):

- chemotherapy administration sheets including dose reductions and reason for dose reduction
- laboratory test results
- other clinically relevant information

The patient will be asked to maintain a diary to be faxed to the research nurse every 4 weeks:

[name] RN
[contact]

All systemic chemotherapy will be administered based on actual body weight if within 20% above or below the ideal body weight. If actual weight is not within 20% of ideal body weight, then ideal body weight will be used to calculate systemic chemotherapy doses.

Ideal body weight will be calculated based upon the following formula:

$$\begin{aligned} \text{IBW (male, in kg)} &= \{(\text{Height in inches} - 60 \} \times 2.3 \} + 50 \\ \text{IBW (female, in kg)} &= \{(\text{Height in inches} - 60 \} \times 2.3 \} + 45.5 \end{aligned}$$

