3.8. Off Treatment Criteria

- Completion of systemic chemotherapy regimen
- Voluntary withdrawal from treatment
- Inability to follow the treatment regimen
- Unacceptable toxicity
- Radiographic or clinical disease progression
- Unwilling or unable to undergo surgical resection for progressive disease
- If the physician deems it is in the patient's best interest not to receive further treatment
- Completion of chemotherapy

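### Section 3.2.6 can be read as stopping FOLFOXIRI for GYMS patients whose peritoneal disease cannot be debulked, with no matching rule in the SA arm

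*Combined protocol and SAP*

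**What the plan says.** Section 3.2 gives the guidelines for the GYMS operation, which Section 3.1.2 places 1–2 weeks after randomization. Within it, Section 3.2.6 deals with patients whose peritoneal disease cannot be reduced to a largest residual nodule of 0.5 cm or less: "patients will be considered ineligible and removed from treatment". The sentence does not mention chemotherapy, and it does not confine itself to surgery.

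Other relevant text:

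- **Off-treatment wording.** Section 3.1.2, on slow recovery from GYMS surgery: "Patients who do not recover within 16 weeks will be taken off treatment and followed for survival". Section 3.5.1 says that patients who miss the recovery window "will be removed from treatment and followed for survival". Section 3.8 has a single off-treatment list for the whole protocol, with entries such as "Unwilling or unable to undergo surgical resection for progressive disease", and no status meaning off surgery only.
- **Eligibility wording.** Section 3.2.7 ties eligibility to a procedure: "To be considered eligible for CHPP and debulking". Section 3.5.1 adds, for both arms, that "patients must meet eligibility requirements prior to beginning chemotherapy".
- **Planned chemotherapy and analysis.** The precis gives FOLFOXIRI to both arms, and Section 3 has GYMS surgery followed by systemic therapy. The precis and Section 3.1.2 specify intention to treat.
- **Data capture.** The note opening Section 3.2 keeps surgical and perioperative details in the medical record and off the CRFs. Section 7.2.1 sends chemotherapy dose reductions and their reasons to the trial database (C3D).

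**The concern.** A patient who has been randomized is in the comparison whatever the surgeon finds. Calling that patient ineligible applies an entry concept after entry. If removal from treatment covers FOLFOXIRI, some GYMS patients lose the chemotherapy common to both arms because of a finding at operation. SA patients have no such operation, and no SA rule stops chemotherapy for the same extent of disease. Under intention to treat, the resulting deaths count against GYMS, so the bias runs against the surgical arm and could hide part of a real benefit.

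Two other things are at stake. A secondary objective (Section 1.1.2) asks whether resection changes the dose and duration of later chemotherapy. An absent course caused by this rule would blur the answer, and the debulking status that explains it would have to be taken from the medical record. For the patient, protocol systemic therapy may be withheld just when surgery has failed to clear the disease.

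**Working it through.** **Which reading does the text support?**

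1. *All protocol treatment ends.* Sections 3.1.2 and 3.5.1 use nearly the same words for patients who receive no protocol chemotherapy and are only followed. Section 3.8 recognises one off-treatment state. No sentence routes an undebulked GYMS patient to FOLFOXIRI.
2. *Surgery only.* Section 3.2.7 speaks of eligibility for debulking and perfusion (CHPP), and the note in Section 3.2 says "Physician discretion will be exercised as necessary to ensure that the specific needs of the patient are met". Section 3.2.6 has no such qualifier of its own.
3. *Does the eligibility note in 3.5.1 decide it?* No. It cannot sensibly re-apply every entry criterion. Inclusion criterion b reads "Metastatic disease must be measurable by CT and/or MRI", with a history of positive washings or carcinomatosis as the alternative. Re-applied after surgery, it would bar a patient whose liver metastases had just been resected. The note probably means fitness and laboratory criteria, but does not say so.

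Reading 1 is the more natural and reading 2 remains open.

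**How large could the effect be?** The documents give neither the share of GYMS patients with peritoneal disease nor the rate of failed debulking, so this is an illustration.

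The plan's own figures come first. With exponential survival, S12 = 0.5^(12/median). Medians of 12 and 20 months (Section 5.4) give 0.5000 and 0.5^0.6 = 0.6598. These are the 50% and 66% in Section 5.4, a planned difference of 16.0 points.

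Inputs:

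- GYMS arm: 68 patients (Section 5.4).
- Peritoneal share: assumed 25% or 50%, so 17 or 34 patients.
- Undebulkable among those: assumed 5% or 10%.
- Affected share u = product of the two: 1.25%, 2.5% or 5%. Times 68, this is 0.85, 1.7 or 3.4 patients.
- Median on FOLFOXIRI: 12 months (Section 5.4, SA arm), or 8 months (assumed, for worse prognosis).
- Median with no chemotherapy: 3–5 months. This is Section 1.2's figure for best supportive care in randomized trials, read as medians.
- Median on off-protocol chemotherapy: 8–10 months (chemotherapy groups of the same trials).

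S12 by median: 3 months, 0.0625; 5, 0.1895; 8, 0.3536; 10, 0.4353; 12, 0.5000.

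Loss in GYMS 12-month survival = u × (S12 on FOLFOXIRI − S12 under the rule). For example, 5% × (0.5000 − 0.0625) = 2.19 points.

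| Comparison (median, months) | u = 1.25% | u = 2.5% | u = 5% |
|---|---|---|---|
| FOLFOXIRI 12 v none 3–5 | 0.39–0.55 | 0.78–1.09 | 1.55–2.19 |
| FOLFOXIRI 8 v none 3–5 | 0.21–0.36 | 0.41–0.73 | 0.82–1.46 |
| FOLFOXIRI 12 v off-protocol 8–10 | 0.08–0.18 | 0.16–0.37 | 0.32–0.73 |
| FOLFOXIRI 8 v off-protocol 8 | 0 | 0 | 0 |

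Entries are percentage points, relative to the same patients receiving protocol FOLFOXIRI. On the surgery-only reading the loss is zero.

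**The case against.** The strongest reply is that the wording is merely ambiguous. The parallel rules in 3.1.2 and 3.5.1 concern patients who have missed the window for starting chemotherapy, so chemotherapy falls away for that reason and not because of the phrase itself. They also provide for survival follow-up, which 3.2.6 does not mention, so the wording is not fully parallel. Section 3.2.7, the discretion clause and the general statements that both arms receive FOLFOXIRI all favour continued chemotherapy.

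In addition, the rule is a backstop. Entry requires disease judged resectable and no worse than P2. Laparoscopy with washings precedes randomization, and mostly hepatic disease is expected (Section 1.2). Nothing forbids chemotherapy off protocol. Intention to treat and lifelong follow-up (Section 3.10) protect the analysis set, and a bias against GYMS cannot produce a false claim for surgery. The largest loss combines the highest assumed shares, a favourable FOLFOXIRI median and the lowest untreated one.

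Most of this stands as a limit on size: few patients, and an effect possibly near zero. It does not remove the defect. Two surgeons could treat identical patients differently and both follow the protocol, and the text supplies no sentence to settle it. That debulking status is missing from the CRFs is inferred from the Section 3.2 note, since the forms are not shown; the main point does not depend on it.

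**Conclusion.** The concern holds. Section 3.2.6 is a post-randomization rule in one arm which, on its most natural reading, withholds the shared chemotherapy in an intention-to-treat survival trial. The surgery-only reading is possible but unstated.

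Under the assumed shares, about 1, 2 or 3 GYMS patients are affected. The loss in GYMS 12-month survival is 0.2–2.2 points with no further chemotherapy and 0–0.7 with off-protocol chemotherapy. At its largest this is 2.19/16.0, about one seventh of the planned difference. No claim is made about power. Confidence is medium, because the reading is an inference and the frequency is unknown. The wording should still be corrected: the consequence for an individual patient is serious and the correction is cheap.

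**What to change.** Amend Section 3.2.6 so that a randomized GYMS patient whose peritoneal disease cannot be debulked to 0.5 cm or less:

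- is recorded as not debulked, and is not called ineligible;
- has no further protocol cytoreduction or CHPP;
- stays on study and in the intention-to-treat set;
- proceeds to protocol FOLFOXIRI on recovery, within the time limits of Section 3.5.1, if fit.

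State in Section 3.5.1 that its eligibility note means fitness and laboratory criteria and does not bar these patients. Add one C3D item for debulking status and subsequent systemic therapy.

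The cost is a short amendment to two sections and one data item. No extra patients are needed, and neither the sample size nor Section 5.4 changes. If the surgery-only meaning was intended all along, the amendment simply writes it down.

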3.3. Intraperitoneal Chemotherapy CHPP

3.3.1. Perfusion

- Two large bore catheters will be inserted through the abdominal wall, one over the right lobe of the liver and one in the pelvis. The abdominal fascia will be closed, and the catheters connected to a perfusion circuit.
- The perfusate passes from a reservoir through a roller pump, heat exchanger, and then into the abdominal cavity.
- Efflux from a second catheter is then recirculated through the reservoir and pump.
- The perfusion flow rate will be maintained at 2.0 L/min and a perfusate volume will be maintained which moderately distends the abdominal cavity correlating with intra abdominal pressures of 5 to 15 mm Hg (2.0 L/m²). Stable perfusion parameters are obtained and the peritoneal cavity is warmed to a minimum of 41°C prior to starting the clock for perfusion time.
- The perfusion will be continued for 35 minutes.
- During the perfusion, constant physical manipulation of the abdomen (shaking) will be maintained for the entire 35 minutes to assure even distribution of the perfusate.
- The heater coil will be maintained at 46-48°C. Peritoneal temperature will be measured continuously by three probes placed immediately beneath the peritoneal surface on either side of the abdomen and in the pelvis.
- The patient's core temperature will be measured with an esophageal probe (which correlates well with pulmonary artery temperatures) and maintained at less than 41°C using a cooling blanket and ice packs around the legs and head.
- At the end of the perfusion, the abdomen will be re-opened and the perfusate irrigated from the abdominal cavity.

3.3.2. Medications

All intraperitoneal drug dosages will be calculated on ideal body weight (IBW). Ideal body weight will be calculated based upon the following formula:

$$\begin{aligned} \text{IBW (male, in kg)} &= \{(\text{Height in inches} - 60) \times 2.3\} + 50 \\ \text{IBW (female, in kg)} &= \{(\text{Height in inches} - 60) \times 2.3\} + 45.5 \end{aligned}$$

- **5-FU (patients randomized to surgery arm)**

Due to pH incompatibility, 5-FU cannot be mixed with oxaliplatin inside the peritoneal cavity; therefore, it will be administered IV, to bathe the tumor and healthy tissue to potentiate oxaliplatin activity. Prior to the beginning of CHPP patients will receive:

- Fluorouracil (5-FU) 400 mg/m² IV in 50 cc over 5 minutes
- Leucovorin 20 mg/m² IV in 50 cc over 5 minutes

- **Oxaliplatin (patients randomized to surgery arm)**
 - Oxaliplatin 460 mg/m² diluted in 2.0 L/m² of D5W via the perfusion circuit

3.4. Postoperative Care

3.4.1. Patient Monitoring

- The patients will be monitored in the Intensive Care Unit for no less than 12 hours after surgical resection.
 - Routine ICU monitoring of vital signs will be performed according to the patient's clinical status.
 - While in the ICU, an attempt to keep urine output greater than 100 cc/hour will be made when physiologically feasible.
 - Patients will be transfused as appropriate to maintain a hemoglobin greater than or equal to 8.0 g/dl, and platelet count greater than 25,000 mm³
- Patients will be discharged from the ICU at the discretion of the treating surgeon and in accordance with the institution policies.
- Following discharge from the ICU, vital signs (blood pressure, temperature, pulse, respirations) will be taken per routine (every 2-6 hours and as clinically indicated).

3.4.2. Continued Postoperative Management:

- Patients will receive routine postoperative care; early ambulation will be encouraged.
- Laboratory evaluations will include:
 - CBC, platelets, and acute panel daily x 4 days and then every third day or as clinically indicated until discharge.
 - Tumor markers for new baseline will be obtained on the day of discharge.
- Patients undergoing CHPP who develop post operative thrombocytopenia and neutropenia will receive standard supportive care as needed.
- X-rays and scans as clinically indicated.

3.4.3. Discharge:

- Total hospitalization may be approximately 7-21 days.
- Patients who are discharged within this time frame should be able to tolerate an oral diet. Patients who have a prolonged hospitalization but are able to tolerate a diet may be discharged with home rehab/physical therapy.
- Within 5 days prior to discharge the following tumor markers should be drawn: AFP, CEA, CRP, CA 19-9, CA 125, CA 15-3, and CA 27-29

